12.2. Safety

12.2.1. Adverse events

Table 12.2.1.1 Summary of adverse events.

Number of patients* with	N	%
Any AE		
Any drug-related* AE		_
Any AE grade ≥ 3		_
Any drug-related AE grade ≥ 3		_
Any SAE		_
Any drug-related SAE		
Deaths associated with AEs		
Deaths associated with drug-related AEs		
Discontinuations associated with AEs		
Discontinuations associated with drug-related AEs		_
Dose delays associated with AEs		_
Dose delays associated with drug-related AEs		_
Dose skipped associated with AEs		

Dose skipped associated with drug-related AEs

Dose reduction associated with AEs

Dose reduction associated with drug-related AEs

(*) Safety Population; (**) Drug related and unknown

Table 12.2.1.2 Summary of hematological laboratory abnormalities.

Number of patients* with**

N

%

Any hematological abnormality

Any hematological abnormality grade ≥ 3

(*) Safety Population.(**) Includes only Hemoglobin, absolute neutrophil count (ANC) and Platelets.

Table 12.2.1.3 Summary of non-hematological laboratory abnormalities.

Number of patients* with**	N	%
Any non-hematological abnormality		
Any hematological abnormality grade ≥ 3		

(*) Safety Population. (**) Includes only ALT, AST, AP, Total Bilirubin, CPK, Creatinine.

- Table 12.2.1.4 Drug-related adverse events. Worst case per patient
- Table 12.2.1.5 Drug-related adverse events occurring in > 10% Worst case per patient.
- Table 12.2.1.6 All adverse events regardless relationship. Worst case per patient.
- Table 12.2.1.7 All adverse events regardless relationship occurring in > 10% Worst case per patient.
- Table 12.2.1.8 Drug-related adverse events. Worst case per cycle.
- Table 12.2.1.9 Drug-related adverse events occurring in > 10% Worst case per cycle.
- Table 12.2.1.10 All adverse events regardless relationship. Worst case per cycle.
- Table 12.2.1.11 All adverse events regardless relationship occurring in > 10% Worst case per cycle.
- Table 12.2.1.12 Listing of AEs leading to death.
- Table 12.2.1.13 Listing of AEs treatment related leading to death.
- Table 12.2.1.14 Listing of AEs leading to dose delay.
- Table 12.2.1.15 Listing of AEs leading to dose reduction.
- Table 12.2.1.16 Listing of AEs leading to dose delay and reduction.

Tables from 12.2.1.4 to 12.2.1.11 will have the following format and grades could be grouped into categories if required.

System Organ Class/ Preferred Term	Grac	le 1	Grad	de 2	Gra	de 3	Gra	de 4	Tot	tal (G1-G4)
	N	%	N	%	N	%	N	%	N	%

System Organ Class 1 (Total)
Preferred Term 1
System Organ Class 2 (Total)

Preferred Term 1

.

Percentages are based on the safety population. Table shows number of distinct patients with events.

Tables from 12.2.1.12 to 12.2.1.16 have the following format*:

Patient ID. Verb	Preferred	Cycle	Grade	•••••	Onset date	End Date
------------------	-----------	-------	-------	-------	---------------	-------------

^(*) Delays and reductions will be checked with information in drug administration.

12.2.2. Grade 3-4 adverse events

Table 12.2.2.1 Listing of patients with grade 3-4 AEs (treatment-related).

Patient Cycle MedDRA preferred term	Verbatim name	Grade	Relationship	Onset date	••••
-------------------------------------	------------------	-------	--------------	---------------	------

^(*)End date, Action taken and serious criteria

Table 12.2.2.2 Listing of patients with grade 3-4 AEs (treatment-related).

Patient Cycle MedDRA Verbatim ID. Cycle preferred name	Grade	Relationship	Onset date	••••
--	-------	--------------	------------	------

^(*)End date, Action taken and serious criteria

12.2.3. Deaths and serious adverse events (SAEs)

All serious adverse events will be listed only for the purpose of reconciliation with the database of the Pharmacovigilance department. The listings provided by the Pharmacovigilance department will be used for the clinical study report.

Table 12.2.3.1 Listing of SAEs.

Patient Cycle MedDRA Verbatim Grade Relationship Onset Ei ID. term

^(*) Also Action taken and serious criteria

Table 12.2.3.2 Listing of all deaths.

Patient ID.	Cycle	MedDRA preferred term	Verbatim name	Grade	Relationship	Onset date	End date
		•					

(*)Taken from death report form.(**)Also Time on treatment: defined as last infusion date plus 30 days, or date of death or subsequent therapy (whichever comes first) minus first infusion date and Time from last dose defined as death date minus last infusion date.

12.3. Laboratory evaluation

12.3.1. Hematological abnormalities

Table 12.3.1.1 Hematological abnormalities during treatment, worst grade per patient.

Parameter*	Gra	de 1	Gra	de 2	Gra	de 3	Gra	de 4	Total (G1-G4)	
	N	%	N	%	N	%	N	%	N	%
Anemia										
Lymphopenia										
Neutropenia										
Thrombocytopenia										

Programming Notes: Percentages are based on the safety population. (*) All hematological abnormalities susceptible to be graded in NCI-CTCAE v4.0.

Table 12.3.1.2 Hematological abnormalities during treatment, worst grade per cycle.

Parameter*	Gra	de 1	Gra	de 2	Gra	de 3	Gra	de 4	Total (G1-G4)
	N	%	N	%	N	%	N	%	N	%
Anemia										
Lymphopenia										
Neutropenia										
Thrombocytopenia										
D	ъ .				0 .		. •			

Programming Notes: Percentages are based on the safety population.

(*) All hematological abnormalities susceptible to be graded in NCI-CTCAE v4.0.

Table 12.3.1.3 Patients with any hematological abnormalities grade 3-4.

Patient Cy	ele Event/	Value	Grade	Onset	Onset	Onset	**	Days with
ID Cy	Parameter Parameter	· at BL*	at BL	day	value	value	•••	Grade 3-4

^(*) Units for Leukocytes, Lymphocytes, Neutrophils and Platelets are in 10⁹/l units in % and Hemoglobin in g/dl. (**) Also Nadir day, nadir value, recovery date, recovery value, recovery grade.

Table 12.3.1.4 Listing of patients and cycles with hematological evaluations missing.

Patient ID	Cycle	Parameter	

Table 12.3.1.5 Time course and recovery from hematological toxicities.

	·	All c	cycles
	N	Median	Range
Neutrophils			
Day of nadir neutrophils count			
Nadir of neutrophils count (/mm ³)			
Day of neutropenia G3-4 onset			
Day of recovery to grade ≤2*			
Number of days with grade 3-4 neutropenia			
Platelets			
Day of nadir platelets count			
Nadir of platelets count (/mm³)			
Day of thrombocytopenia G3-4 onset			
Day of recovery to grade ≤2*			
Number of days with grade 3-4 thrombocytopenia			

Programming notes: (*) Denominator = No of cycles with Grade 3-4. Also recovery to grade 1 or an specific value if required.

Table 12.3.1.6 Baseline grade and evolution of hematological toxicities.

			Wo	orst grac	de per p	atient d	uring t	reatmen	t	
Baseline	Gra	ade 0	Grade 1		Gra	Grade 2		Grade 3		le 4
Dasenne	N	%	N	%	N	%	N	%	N	%
Anemia										
Grade 0										
Grade 1										
Grade 2										
Grade 3										
Grade 4										
Neutropenia										
Grade 0										
Grade 1										
Grade 2										
Grade 3										
Grade 4										

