8.1. Missing value management

In case of missing values in the determination of protocol deviations (for instance, time from last anticancer treatment to start of treatment with Zalypsis®) the most conservative approach will be taken for the evaluation.

The cycles with missing information regarding laboratory values or adverse events will be subtracted from the denominator of the tables.

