12.3.2. Biochemical abnormalities

Table 12.3.2.1 Biochemical abnormalities during treatment, worst grade per patient.

Parameter*	Gra	de 1	Gra	de 2	Gra	de 3	Gra	de 4	Total (G1-G4)
Parameter.	N	%	N	%	N	%	N	%	N	%
AST										
ALT										
*										

Programming Notes: Percentages are based on the safety population. (*) All biochemical abnormalities susceptible to be graded by NCI-CTCAE v4.0.

Table 12.3.2.2 Biochemical abnormalities during treatment, worst grade per cycle.

Doromotor*	Gra	de 1	Gra	de 2	Gra	de 3	Gra	de 4	Total (G1-G4)
Parameter*	N	%	N	%	N	%	N	%	N	%
AST										
ALT										
*										

Programming Notes: Percentages are based on the safety population. (*) All biochemical abnormalities susceptible to be graded by NCI-CTCAE v4.0.

Table 12.3.2.3 Supportive listing: Patients with any biochemical abnormalities grade 3-4.

Patient	Cycle	Event/	Value	Grade	Onset	Onset	*	Days with
ID	Cycle	Parameter	at BL	at BL	day	value	••••	Grade 3-4

(*) Nadir day, nadir value, recovery date, recovery value and recovery grade to grade ≤ 2 .

Table 12.3.2.4 Listing of patients and cycles with biochemical evaluations missing.

	Patient ID	Cycle	Lab test
--	------------	-------	----------

Table 12.3.2.5 Time course and recovery from biochemical toxicities.

		All cyc	les
	N	Median	Range
ALT			
Day of peak ALT count			
Peak of ALT count (/mm ³)			
Day of ALT G3-4 onset			
Day of recovery to grade ≤2			
Number of days with grade 3-4 ALT increase			
AST			

Day of peak AST count Peak of AST count (/mm³) Day of AST G3-4 onset

Day of recovery to grade ≤2*

Number of days with grade 3-4 AST increase

Programming notes: (*) Denominator= Number of cycles with Grade 3-4. Also recovery to grade 1 if required.

Table 12.3.2.6 Baseline grade and evolution of biochemical toxicities.

			Wo	orst grac	de per p	atient d	luring t	reatmen	t	
Dagalina	Grade 0		Grade 1		Gra	de 2 Gra		le 3	Gra	de 4
Baseline	N	%	N	%	N	%	N	%	N	%
AST										
Grade 0										
Grade 1										
Grade 2										
Grade 3										
Grade 4										
ALT										
Grade 0										
Grade 1										
Grade 2										
Grade 3										
Grade 4										

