12.3.3. Other metabolic abnormalities

Table 12.3.3.1 Metabolic abnormalities during treatment, worst grade per patient

Parameter*	Gra	ade 1	Gra	de 2	Gra	de 3	Gra	de 4	Total (G1-G4)
rarameter.	N	%	N	%	N	%	N	%	N	%
Hyperglycemia										
(*) All metabolic	oaramet	ers susc	eptible t	o be gra	ded as p	er NCI-C	CTCAE	v4.0		

Table 12.3.3.2 Metabolic abnormalities during treatment, worst grade per cycle.

Parameter*	Gra	ade 1	Gra	de 2	Gra	de 3	Gra	de 4	Total (G1-G4)
rarameter.	N	%	N	%	N	%	N	%	N	%
Hyperglycemia										

^(*) All metabolic parameters susceptible to be graded as per NCI-CTCAE v4.0

Table 12.3.3.3 Metabolic abnormalities grade per cycle.

Doromotor*	Gra	ade 1	Gra	ide 2	Gra	ide 3	Gra	de 4	Total (G1-G4)
Parameter*	N	%	N	%	N	%	N	%	N	%
Hyperglycemia										
••••										

^(*) All metabolic parameters susceptible to be graded as per NCI-CTCAE v4.0

Table 12.3.3.4 Listing of patients and cycles with metabolic evaluations missing.

Patient ID.	Cycle	Lab. test
	 	 

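### The SAP footnotes its per-cycle laboratory and adverse-event tables with a patient-based denominator, against the cycle-based denominator in SAP 8.1

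*SAP*

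**What the plan says.** **Laboratory tables.** SAP 12.3.1 contains a shell titled "Table 12.3.1.2 Hematological abnormalities during treatment, worst grade per cycle", with the note "Percentages are based on the safety population". SAP 12.3.2 contains "Table 12.3.2.2 Biochemical abnormalities during treatment, worst grade per cycle", with the note "Programming Notes: Percentages are based on the safety population. (*) All biochemical abnormalities susceptible to be graded by NCI-CTCAE v4.0". The matching per-patient shells (12.3.1.1 and 12.3.2.1) carry the same denominator note. SAP 12.3.3 contains "Table 12.3.3.2 Metabolic abnormalities during treatment, worst grade per cycle" and a further per-cycle table, 12.3.3.3. Neither states a denominator.

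**Adverse-event tables.** SAP 12.2.1 lists four per-patient tables (12.2.1.4 to 12.2.1.7) and four worst-case-per-cycle tables (12.2.1.8 to 12.2.1.11), and gives all eight a single shell. Its note reads "Percentages are based on the safety population. Table shows number of distinct patients with events".

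**General rules.** SAP 4.1.2 defines the safety population as patients with at least one full or partial infusion. SAP 8.1 states: "The cycles with missing information regarding laboratory values or adverse events will be subtracted from the denominator of the tables". SAP 7.4.3 promises toxicity profiles both per patient and per cycle. It gives the unit for the worst grade twice, once as patient and cycle and once as patient and infusion.

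**The concern.** A table titled per cycle needs cycles in the numerator and in the denominator. The shell notes supply patients in the denominator and, for adverse events, in the numerator as well. A programmer cannot follow these notes and SAP 8.1 literally at the same time, because missing cycles can only be subtracted from a count of cycles.

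The SAP does not use this form everywhere. It writes out cycle denominators for dose delays (12.1.2) and dose reductions (12.1.4), and takes skipped doses as a percentage of all cycles (12.1.3). The per-cycle toxicity shells are the exception.

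At stake is the per-cycle part of the safety description, and safety is a secondary objective. Per-cycle laboratory rates could be inflated, and the per-cycle adverse-event tables could hold no per-cycle information.

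**Working it through.** The shells are empty, so there is no figure of the plan's own to reproduce. The check is on what the notes produce if followed.

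**Inputs.** The unit of the safety population is the patient (SAP 4.1.2). The table titles, notes and the 8.1 rule are as quoted. Mean cycles per patient in this trial, m, is not given in the documents, so a range of 1 to 4 is assumed. The planned 29 evaluable patients (SAP 6.1) serve as an illustrative safety population.

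**Step 1: laboratory tables, if N counts cycles.** Let n be patients, C cycles and E cycles with the abnormality. Write q = E/C for the true per-cycle share and m = C/n. The printed figure is

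100 × E/n = 100 × q × m.

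It exceeds 100% when q > 1/m.

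| Assumed m | Printed when q = 25% | Printed when q = 50% | Passes 100% when q exceeds |
|---|---|---|---|
| 1 | 25% | 50% | never |
| 1.5 | 37.5% | 75% | 66.7% |
| 2 | 50% | 100% | 50% |
| 3 | 75% | 150% | 33.3% |
| 4 | 100% | 200% | 25% |

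The result does not depend on n. With cycles as the denominator the maximum is 100%.

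One case needs no assumed mean. Protocol 1.2.5.1.1 reports anemia in all phase I patients at the dose used here. If that recurs, every patient contributes at least one affected cycle, so E ≥ n and the anemia total in Table 12.3.1.2 prints at least 100%. It passes 100% as soon as one patient is anemic in a second cycle.

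**Step 2: adverse-event tables, as footnoted.** The numerator is distinct patients and the denominator is patients, so no single event can exceed 100%. The total for any event is the same as in the per-patient table. Hence Table 12.2.1.9 would select the same events as 12.2.1.5, and 12.2.1.11 the same as 12.2.1.7.

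The selection differs from a true per-cycle cut. Take 29 patients and an assumed mean of 2 cycles, which is 29 × 2 = 58 cycles:

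- An event in 3 patients, one cycle each: 3/29 = 10.3% of patients, so it is listed, but 3/58 = 5.2% of cycles.
- An event in 2 patients, three cycles each: 2/29 = 6.9% of patients, so it is not listed, but 6/58 = 10.3% of cycles.

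**Step 3: against SAP 8.1.** Under 8.1 the denominator is C less the cycles with missing information. Under the notes it is n. The two have different units and agree only in the trivial case of one cycle per patient with nothing missing.

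**Step 4: metabolic tables.** Tables 12.3.3.2 and 12.3.3.3 state no denominator, so there is no contradiction there, only a gap that 8.1 would fill.

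**The case against.** The strongest answer is that the safety population here names an analysis set: the cycles given to patients in that set. SAP 8.1 supports this, as does SAP 7.4.5, which calculates hematological abnormalities over all cycles. The SAP also says each final table will have its own header and footnotes, so these may be notes carried over from the per-patient shells and not a chosen denominator. For the two laboratory tables this reading removes the contradiction, and a carry-over is the more plausible origin. It does not rescue the adverse-event shell, where the note says outright that distinct patients are counted.

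It can also be said that a figure above 100% would be noticed on output. That is true, but a figure inflated below 100% would not be: 25% of cycles at a mean of 2 prints as 50%.

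Two stronger readings are tempting, and the documents do not support them.

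- A reader might infer that the adverse-event tables would also exceed 100%. Protocol 1.2.5.1.1 gives nausea in 77.4% and vomiting in 62.3% of cycles, which fit 41/53 and 33/53; over 24 patients those counts would be 170.8% and 137.5%. But these are adverse events. Under the SAP's note they would print as distinct patients: 21/24 = 87.5% and 20/24 = 83.3%. The 53 cycles are also an inference. Protocol 1.2.5.1 prints a total of 24 cycles at that dose, although that does not fit 24 patients with a median of 2 cycles.
- A reader might infer that the 10% cut falls to about 4.5% of cycles (10% of 24 is 2.4, and 2.4/53 = 4.5%). That holds only if N counts cycles, which the adverse-event note rules out.

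**Conclusion.** The notes are wrong as written for six tables, in two different ways. In Tables 12.3.1.2 and 12.3.2.2, if N counts cycles, the percentage is the true per-cycle share multiplied by mean cycles per patient and can exceed 100%. The factor for this trial is unknown; at an assumed mean of 2 it doubles every rate. In Tables 12.2.1.8 to 12.2.1.11, percentages stay within 100% but describe patients, so the promised per-cycle incidence is missing and the two tables with a 10% cut select on the wrong unit. Both notes conflict with SAP 8.1 and SAP 7.4.3.

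The laboratory conclusion rests on reading the safety population literally as patients; the adverse-event conclusion does not depend on that reading. The impact is confined to descriptive safety tables. The per-patient tables have suitable denominators, and ORR and the two-stage decision rule are untouched.

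**What to change.** - In Tables 12.3.1.2, 12.3.2.2 and 12.2.1.8 to 12.2.1.11, state that N is the number of cycles with the event at that worst grade. State that the denominator is cycles given to safety-population patients, less cycles with missing laboratory or adverse-event information under SAP 8.1.
- Split the shared adverse-event shell, and delete the distinct-patients wording from the per-cycle half. Apply the 10% cut in 12.2.1.9 and 12.2.1.11 to the cycle percentage.
- Add the same denominator to Tables 12.3.3.2 and 12.3.3.3.
- In SAP 7.4.3, reconcile the two statements of the unit (patient and cycle; patient and infusion).
- Keep the safety-population denominator for the per-patient tables.

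The cost is footnotes in eight tables and one sentence in 7.4.3. No new data are needed for the laboratory denominators, since the SAP already plans listings of cycles with missing evaluations (12.3.1.4, 12.3.2.4 and 12.3.3.4).

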12.3.2. Biochemical abnormalities

Table 12.3.2.1 Biochemical abnormalities during treatment, worst grade per patient.

Parameter*	Gra	de 1	Gra	de 2	Gra	de 3	Gra	de 4	Total (G1-G4)
Parameter.	N	%	N	%	N	%	N	%	N	%
AST										
ALT										
*										

Programming Notes: Percentages are based on the safety population. (*) All biochemical abnormalities susceptible to be graded by NCI-CTCAE v4.0.

Table 12.3.2.2 Biochemical abnormalities during treatment, worst grade per cycle.

Doromotor*	Gra	de 1	Gra	de 2	Gra	de 3	Gra	de 4	Total (G1-G4)
Parameter*	N	%	N	%	N	%	N	%	N	%
AST										
ALT										
*										

Programming Notes: Percentages are based on the safety population. (*) All biochemical abnormalities susceptible to be graded by NCI-CTCAE v4.0.

Table 12.3.2.3 Supportive listing: Patients with any biochemical abnormalities grade 3-4.

Patient	Cycle	Event/	Value	Grade	Onset	Onset	*	Days with
ID	Cycle	Parameter	at BL	at BL	day	value	••••	Grade 3-4

(*) Nadir day, nadir value, recovery date, recovery value and recovery grade to grade ≤ 2 .

Table 12.3.2.4 Listing of patients and cycles with biochemical evaluations missing.

	Patient ID	Cycle	Lab test
--	------------	-------	----------

Table 12.3.2.5 Time course and recovery from biochemical toxicities.

		All cyc	les
	N	Median	Range
ALT			
Day of peak ALT count			
Peak of ALT count (/mm ³)			
Day of ALT G3-4 onset			
Day of recovery to grade ≤2			
Number of days with grade 3-4 ALT increase			
AST			

Day of peak AST count Peak of AST count (/mm³) Day of AST G3-4 onset

Day of recovery to grade ≤2*

Number of days with grade 3-4 AST increase

Programming notes: (*) Denominator= Number of cycles with Grade 3-4. Also recovery to grade 1 if required.

Table 12.3.2.6 Baseline grade and evolution of biochemical toxicities.

			Wo	orst grac	de per p	atient d	luring t	reatmen	t	
Dagalina	Grade 0		Grade 1		Gra	de 2 Gra		le 3	Gra	de 4
Baseline	N	%	N	%	N	%	N	%	N	%
AST										
Grade 0										
Grade 1										
Grade 2										
Grade 3										
Grade 4										
ALT										
Grade 0										
Grade 1										
Grade 2										
Grade 3										
Grade 4										

12.3.3. Other metabolic abnormalities

Table 12.3.3.1 Metabolic abnormalities during treatment, worst grade per patient

Parameter*	Gra	ade 1	Gra	de 2	Gra	de 3	Gra	de 4	Total (G1-G4)
rarameter.	N	%	N	%	N	%	N	%	N	%
Hyperglycemia										
(*) All metabolic	oaramet	ers susc	eptible t	o be gra	ded as p	er NCI-C	CTCAE	v4.0		

Table 12.3.3.2 Metabolic abnormalities during treatment, worst grade per cycle.

Parameter*	Gra	ade 1	Gra	de 2	Gra	de 3	Gra	de 4	Total (G1-G4)
rarameter.	N	%	N	%	N	%	N	%	N	%
Hyperglycemia										

^(*) All metabolic parameters susceptible to be graded as per NCI-CTCAE v4.0

Table 12.3.3.3 Metabolic abnormalities grade per cycle.

Doromotor*	Gra	ade 1	Gra	ide 2	Gra	ide 3	Gra	de 4	Total (G1-G4)
Parameter*	N	%	N	%	N	%	N	%	N	%
Hyperglycemia										
••••										

^(*) All metabolic parameters susceptible to be graded as per NCI-CTCAE v4.0

Table 12.3.3.4 Listing of patients and cycles with metabolic evaluations missing.

Patient ID.	Cycle	Lab. test
	 	 

12.4. Vital Signs

Table 12.4.1 Vital signs.

Vital Signs	Baseline	Cycle 1	Cycle 2	•••	Cycle (X)
PS					
BPS (mmHg)					
BPD (mmHg)					
Weigth (Kg)			_	_	

12.5. Prophylactic and concomitant medication during treatment

Table 12.5.1 Patients who received prophylactic medication.

No patients with Adequate prophylaxis	%	N Cycles administered	No Cycles with adequate prophylaxis	%
---------------------------------------	---	--------------------------	-------------------------------------	---

Table 12.5.2 Prophylactic therapy by patient.

Patient ID	Cycles	Dexamethasone Y/N	Dose	Ondansetron Y/N	Dose	Other	Specify
	Cycle 1						
	Cycle 2						
	Cycle n						

Table 12.5.3 Agents of concomitant therapy started during treatment.

Concomitant medication (ATC1/ATC2/ATC4)						
System(ATC1)	Indication(ATC2)	Agents(ATC4)	N	%		
Alimentary tract and metabolism	Stomatological preparations	Antiinfectives for local oral treat. Other agents for				
	Antiacids					

Table 12.5.4 Concomitant medication characteristics during treatment.

	Total (N	N=XX)
	N	%
Number of Systems (ATC1)		
1		
2		
3		
> 3		
Number of indications (ATC2)		

Number of indications (ATC2)

1 2

3

> 3					
lumber of agents	(ATC4)				
2					
3					
> 3					
Programming Not	es: Percentage	e is based on tot	al patient incl	uded.	
Table 12.5.5 Sum	nmary of conc	omitant medica	tion during tre	atment.	
Concomitant med (ATC1/ATC2/AT			N Me	dian Min	Max
Number of system	ns involved (A	TC1)			
Number of indicat		` ′			
Number of agents	involved (AT	CC4)			
12.6. Cardiac s	eafaty				
Table 12.6.1 Listi	•	with Cardiac A	Es and charac	eteristics	
Patient		MedDRA	Grade		
ID.	Cycle*	PT	**	Relationship	***
		d. **According	to NCI-CTCA	AE v.4.0 *** Also	Seriousness
Criteria, Action ta	ken			AE v.4.0 *** Also	Seriousness
*Cycle in witch the Criteria, Action to Table 12.6.2 Listing Patient ID	ken				Seriousness Cycle (X)
Criteria, Action ta Table 12.6.2 Listi	ken ing of ECG ev	olution per pati	ent.		
Criteria, Action ta Table 12.6.2 Listi Patient ID	ken ing of ECG ev Baseline	volution per pati Cycle 1	ent. Cycle		
Criteria, Action ta Table 12.6.2 Listi	ken ing of ECG ev Baseline ing of patients	volution per pati Cycle 1	ent. Cycle ECG.		
Criteria, Action ta Table 12.6.2 Listi Patient ID Table 12.6.3 Listi	ken ing of ECG ev Baseline ing of patients	Cycle 1 S with abnormal esult at baselin	ent. Cycle ECG.	2	Cycle (X)
Criteria, Action ta Table 12.6.2 Listi Patient ID Table 12.6.3 Listi Patient ID (*) If applicable in	ken ing of ECG ev Baseline ing of patients Renformation ob	Cycle 1 S with abnormal esult at baselin tained from AE	ent. Cycle ECG.	2	Cycle (X)
Criteria, Action ta Table 12.6.2 Listi Patient ID Table 12.6.3 Listi Patient ID	ken ing of ECG ev Baseline ing of patients Renformation ob	Cycle 1 Cycle 1 with abnormal esult at baselin tained from AE LVEF (%).	ent. Cycle ECG. e	2 Cycle	Cycle (X) Specify*
Criteria, Action ta Table 12.6.2 Listi Patient ID Table 12.6.3 Listi Patient ID (*) If applicable in	ken ing of ECG ev Baseline ing of patients Renformation ob	Cycle 1 S with abnormal esult at baselin tained from AE	ent. Cycle ECG.	2	Cycle (X)
Criteria, Action ta Table 12.6.2 Listi Patient ID Table 12.6.3 Listi Patient ID (*) If applicable in	ken ing of ECG ev Baseline ing of patients Renformation ob	Cycle 1 Cycle 1 with abnormal esult at baselin tained from AE LVEF (%).	ent. Cycle ECG. e	2 Cycle	Cycle (X) Specify*
Criteria, Action ta Table 12.6.2 Listi Patient ID Table 12.6.3 Listi Patient ID (*) If applicable in	ken ing of ECG ev Baseline ing of patients R nformation ob	Cycle 1 Gwith abnormal esult at baselin tained from AE LVEF (%).	ent. Cycle ECG. e Median	2 Cycle	Cycle (X) Specify*
Criteria, Action ta Table 12.6.2 Listi Patient ID Table 12.6.3 Listi Patient ID (*) If applicable in Table 12.6.4 Med	ken ing of ECG ev Baseline ing of patients R nformation ob	Cycle 1 Gwith abnormal esult at baselin tained from AE LVEF (%).	ent. Cycle ECG. e Median	Cycle Min	Cycle (X) Specify*
Criteria, Action ta Table 12.6.2 Listi Patient ID Table 12.6.3 Listi Patient ID (*) If applicable in Table 12.6.4 Med Table 12.6.5 Listi	ing of ECG events and the second seco	Cycle 1 with abnormal esult at baselin tained from AE LVEF (%). N ECG evolution p	ent. Cycle ECG. e Median per patient.	Cycle Min	Cycle (X) Specify* Max

Table 12.6.6 LVEF characteristics per patient.

Patient ID.	Value at baseline	Minimum value	Cycle (minimum value)

Table 12.6.7 Median change in Troponin I.

	N	Median	Min	Max
Baseline to nadir value (%)				
Baseline to last value (%)				

(*) Also tables in (x ULN) values if applicable.

Table 12.6.8 Listing of Troponin I evolution.

Patient ID.	Value* at Baseline (ng/ml)	Cycle 1	Cycle 2		Cycle (X)
-------------	----------------------------	---------	---------	--	-----------

(*) Also tables in (x ULN) values if applicable

Table 12.6.9 Troponin I characteristics per patient.

Patient ID.	Value* at baseline (ng/ml)	Maximum value	Cycle (maximum value)
-------------	-------------------------------	---------------	-----------------------

(*) Also tables in (x ULN) values if applicable

